4.2.7.3. Psoriasis Area and Severity Index (PASI)

The PASI is a measure of psoriatic disease severity taking into account qualitative lesion characteristics (erythema, thickness, and scaling) and degree of skin surface area involvement on defined anatomical regions. Psoriasis Area and Severity Index scores range from 0 to 72, with higher scores reflecting greater disease severity. Erythema, thickness, and scaling are scored on a scale of 0 (none) to 4 (very severe) on 4 anatomic regions of the body: head, trunk, upper limbs, and lower limbs. Degree of involvement on each of the 4 anatomic regions is scored on a scale of 0 (no involvement) to 6 (90% to 100% involvement). The total qualitative score (sum of erythema, thickness, and scaling scores) is multiplied by the degree of involvement for each anatomic region and then multiplied by a constant. These values for each anatomic region are summed to yield the PASI score. The PASI score will be set to missing if any severity score or degree of involvement is missing.

PASI scores will be presented with one digit after the decimal point. For post-baseline visits, PASI score change and percent change from baseline will be derived. PASI score percent change will be rounded to integers.

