# **Appendix C:** Psoriasis Area and Severity Index (PASI)

\* Round all calculations to 1 decimal place

STEP A. Please write in the appropriate number for r below:	ows 1 - 3	using the so	cale	
0 = None 1 = Slight 2 = Moderate 3 = Severe 4	= Very S	Severe		
	HEAD	TRUNK	UPPER LIMBS	LOWER LIMBS
1. Erythema				
2. Thickness				
3. Scaling				
4. TOTAL Each Column				
STEP B. Enter the number of hands the psoriasis cover	rs on eac	h body are	a	
	HEAD	TRUNK	UPPER LIMBS	LOWER LIMBS
5. Number of Hands				
6. Area (% of total BSA)	10	30	20	40
STEP C. Calculate % of involvement:				
7. % of each region involved [(Row 5 ÷ Row 6) x 100*]				
8. TOTAL BSA (sum of # of hands from row 5)				
STEP D. Select Degree of Involvement using value in R	low 7:			
0 = No involvement				
1 = <10%				
2 = 10 < 30%				
3 = 30 < 50%				
4 = 50 < 70%				
5 = 70 < 90%				
6 = 90 < 100%				
9. Degree of Involvement (0-6) of each region				
STEP E. Calculate PASI (Row 4 x Row 6 x Row 9) ÷ 1	 00*			
10. PASI for each body region				
11. TOTAL PASI (sum of Row 10 subscores)				

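### SAP 4.2.7.3 voids the whole PASI total for any blank component, with no exception for a region whose sub-score is zero by the formula (minor)

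*SAP*

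**What the plan says.** SAP 4.2.7.3 gives one missing-data rule for PASI: "The PASI score will be set to missing if any severity score or degree of involvement is missing". It makes no exception for a region without psoriasis.

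The same section defines the score as a sum over four regions. In each, the sum of the three severity scores "is multiplied by the degree of involvement for each anatomic region and then multiplied by a constant". Protocol Appendix C gives the same product and then divides by 100: "STEP E. Calculate PASI (Row 4 x Row 6 x Row 9". Row 4 is the severity sum, Row 6 the region weight (10, 30, 20 or 40) and Row 9 the degree of involvement.

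Both factors can be zero. Degree of involvement is "scored on a scale of 0 (no involvement) to 6 (90% to 100% involvement". For severity, the SAP says "Erythema, thickness, and scaling are scored on a scale of 0 (none) to 4 (very severe) on 4 anatomic regions", and the Appendix C form asks for a number coded "0 = None 1 = Slight 2 = Moderate 3 = Severe 4" and so on, with a column for each region.

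Change from baseline in total PASI at Week 16 is the third secondary endpoint and fourth in the fixed sequence (SAP 6.2). It is analysed by MMRM without explicit imputation (SAP 6.4.2).

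**The concern.** A missing-data rule should mark a total as missing when it cannot be known. This one also does so when the total is known. The score has 12 severity entries and 4 degrees of involvement, and one blank among the 16 removes the visit's PASI, even where the blank is multiplied by zero.

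The situation is not exotic here. Entry requires BSA of 2-15% (Protocol 4.2), so regions without lesions are likely from baseline onward. The form also asks for the severity rows before it asks for hands and area, so a rater has to enter three severity scores for a region with nothing to grade.

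The SAP treats a comparable gap differently elsewhere. Under SAP 4.2.7.6 a single unanswered DLQI item is scored 0, although its true value is unknown.

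At stake is the completeness of the Week 16 PASI change, after which BSA ≤ 3%, itch, scalp and DLQI are tested. If blanks fell mainly in regions that had just cleared, the lost totals would tend to be good outcomes. SAP 6.4.2 has no missing-data sensitivity analysis for PASI that might reveal this, although Protocol 9.6.1.2 plans an ANCOVA with LOCF for continuous endpoints.

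**Working it through.** **Inputs.** Severity items 0-4, so severity sums run 0-12; degrees 0-6; weights 10 (head), 30 (trunk), 20 (upper limbs), 40 (lower limbs). All are from Protocol Appendix C and SAP 4.2.7.3.

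**Formula.** PASI = Σ (severity sum × weight × degree) / 100.

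**1. The plan's own range.** Maximum: 12 × (10 + 30 + 20 + 40) × 6 / 100 = 72. Minimum: 0. This agrees with "Psoriasis Area and Severity Index scores range from 0 to 72".

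**2. Degree 0, severity blank.** Let trunk, upper and lower limbs each have severity sum 5 and degree 1, and let the head have degree 0.
- Trunk 5 × 30 × 1 / 100 = 1.5; upper limbs 5 × 20 × 1 / 100 = 1.0; lower limbs 5 × 40 × 1 / 100 = 2.0.
- Head: h × 10 × 0 / 100 = 0 for every h from 0 to 12.
- Total 4.5 in all 13 cases. Under the SAP rule it is missing if one head severity item is blank.

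**3. Severity all 0, degree blank.** Head: 0 × 10 × d / 100 = 0 for every d from 0 to 6. The total is again 4.5, and again missing under the rule.

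**4. A truly unknown total.** Head degree 1, two severity items summing to 4, the third blank. The head contributes (4 to 8) × 10 × 1 / 100 = 0.4 to 0.8, so the total lies between 4.9 and 5.3. Setting this to missing is reasonable.

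**5. Can eligible subjects have clear regions?** Yes. Lower limbs alone, severity sum 5 and degree 1, give 5 × 40 / 100 = 2.0, and trunk alone with severity sum 7 gives 7 × 30 / 100 = 2.1. Both meet the PASI entry minimum of 2 with three clear regions.

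**6. How many totals are lost?** The documents do not allow this to be computed. As illustration only, assume regions are involved independently with probabilities 0.45, 0.70, 0.80 and 0.85. The share of subjects with at least one uninvolved region is 1 − 0.45 × 0.70 × 0.80 × 0.85 = 1 − 0.214 = 79%. If 5% of those forms have a blank, 0.79 × 5% ≈ 4% of totals are lost; at 20%, about 16%; at 0%, none.

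**7. Would the estimate move?** Only if blanks follow response. Assume mean change −5 in subjects with a newly cleared region (share s) and −2 in the rest, with a fraction b of the former lost. The observed arm mean is [s(1 − b)(−5) + (1 − s)(−2)] / [s(1 − b) + (1 − s)].

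| b | s = 20% | s = 40% | difference between the two |
|---|---|---|---|
| 0% | −2.60 | −3.20 | −0.60 |
| 10% | −2.55 | −3.12 | −0.57 |
| 30% | −2.45 | −2.95 | −0.51 |
| 50% | −2.33 | −2.75 | −0.42 |

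If s = 20% stands for placebo and s = 40% for apremilast, the last column is the treatment difference, and it shrinks toward zero. Every input here is assumed. These are plain observed means, not an MMRM fit, which would use earlier visits as well. If blanks are unrelated to outcome, for example in regions never involved, the expected means do not move and only precision is lost.

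**The case against.** The strongest reply is that the problem may never arise. Appendix C asks for a number in each severity row and supplies 0 for a clear region, so a form completed as instructed has no blank there. No text allows severity items to be skipped when a region is uninvolved. Protocol 14.2 provides programmed edit checks with discrepancies resolved in the database, and Protocol 15.1 adds source data verification. Eligibility needs a PASI of 2-15 at Screening and Baseline, so sites must score the form before randomization and baseline loss is unlikely. The rule is also prespecified and unambiguous.

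Most of this stands and sets the size of the point. It does not remove it, because a missing-data rule exists for forms that are not completed as instructed. The documents also do not say that blank PASI items are among the edit checks.

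A reader might go further and infer that known PASI values are in fact being lost, mainly in subjects who cleared a region and so more often on apremilast, with the later tests in the sequence at risk. The documents do not support this. They give no blank rate and no sign of where blanks would fall. At a BSA of 2-15%, many uninvolved regions will have been clear since baseline, which has no necessary link to response or arm. Nor can it be said that the MMRM leaves such bias untouched: it draws on earlier PASI visits, and what would remain has not been tested.

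**Conclusion.** The narrow point holds and follows from the formula alone. When a region's sub-score is zero because its degree of involvement is 0 or all its severity scores are 0, a blank in the other factor leaves the total fully determined, and SAP 4.2.7.3 discards it.

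The impact is unknown and probably small, and it is zero if the eCRF forces an entry. Selective loss is possible but not shown. If it did occur through newly cleared regions, and apremilast cleared more of them, the bias would run toward no effect and would not favour a false claim of benefit. No consequence for the later tests in the sequence has been demonstrated.

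The reach is limited to PASI-based analyses: the Week 16 PASI change and, in principle, the baseline PASI subgroup. The primary sPGA endpoint, the BSA endpoints and the sample size do not depend on the PASI total. This is a minor improvement at almost no cost.

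**What to change.** Before the Week 16 unblinding, which is also the SAP's own deadline for being finalised and signed (SAP 2), replace the last sentence of the first paragraph of SAP 4.2.7.3 with a rule to this effect:

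- If a region's degree of involvement is 0 (0 hands), or all three of its severity scores are 0, its sub-score is 0, even if its other entries are blank.
- Total PASI is missing only if another region lacks a severity score or its degree of involvement.

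Keep issuing site queries for blank entries, so that the derivation does not replace a correction the site could make. It would also help to state whether the eCRF requires an entry for every region. If it does, the new rule is harmless and will not be triggered.

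The cost is one sentence in the SAP and one line of derivation code. Making the change now avoids a post hoc change to the derivation of a sequence-tested endpoint if blanks are found after unblinding.

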4.2.7.4. Whole Body Itch Numeric Rating Scale (NRS) Assessment

The whole body itch NRS assessment is a tool designed to measure the amount of whole body itch due to psoriasis by circling a number on a scale from 0 to 10. Subjects will be asked to assess their worst level whole body itch in the past 24 hours and select a number on a scale of 0 to 10, where "0" represents no itching, and "10" represents the worst itch imaginable.

For a post baseline visit, the whole body itch NRS response is defined as ≥ 4 points reduction (improvement) from baseline in the NRS score for subjects with baseline score 4 or higher. Change from baseline in the NRS score will also be derived.

4.2.7.5. Scalp Physician Global Assessment (ScPGA)

The ScPGA is a measurement of overall scalp involvement. The ScPGA is a 5-point scale that assesses three dimensions (Plaque Elevation, Scaling, and Erythema) on a scale of 0 (clear), 1 (almost clear), 2 (mild), 3 (moderate), to 4 (severe).

For a post baseline visit, the ScPGA response is defined as achieving ScPGA global assessment of 0 (clear) or 1 (almost clear) with at least a 2-point reduction from baseline among subjects with baseline ScPGA score \geq 2. Change from baseline in the ScPGA score will also be derived.

4.2.7.6. Dermatology Life Quality Index (DLQI)

The DLQI was developed as a simple, compact, and practical questionnaire for use in a dermatology clinical setting to assess limitations related to the impact of skin disease. The instrument contains 10 items dealing with the subject's skin. With the exception of Item Number 7, the subject responds on a four-point scale, ranging from "Very Much" (score 3) to "Not at All" or "Not relevant" (score 0). Item Number 7 is a multi-part item, the first part of which ascertains whether the subject's skin prevented them from working or studying (Yes or No, scores 3 or 0 respectively), and if "No," then the subject is asked how much of a problem the skin has been at work or study over the past week, with response alternatives being "A lot," "A little," or "Not at all" (scores 2, 1, or 0 respectively). The DLQI total score is derived by summing all item scores, which has a possible range of 0 to 30, with 30 corresponding to the worst quality of life, and 0 corresponding to the best.

If one of the 10 items is left unanswered, it is scored 0 and the scores are summed and expressed as usual out of a maximum of 30. If two or more of the ten items are left unanswered, DLQI total score will be left missing. When using sub-scales, if the answer to one item in a sub-scale is missing, the score is set to missing for that sub-scale.

DLQI total score and change from baseline will be derived.

4.2.8 Derivations of Safety Endpoints

Baseline definition for all safety endpoints is given in Section 5.3. Change from baseline is calculated as post-baseline visit value minus the baseline value. Handling of time points is described in Section 5.4.

4.2.8.1. Treatment-emergent Adverse Event

An AE is a treatment-emergent AE (TEAE) if the AE start date is

- On or after the date of the first dose of investigational product (IP) and no later than 28 days after the last dose of IP for subjects who have completed study treatment or have discontinued early by the time of database cut, or
- On or after the date of the first dose of IP for subjects who are ongoing with study treatment at the time of database cut.

If the treatment-emergent status of an AE is unclear due to a missing/incomplete start date, it will always be considered treatment-emergent, unless shown otherwise by data. Date imputation rules for missing AE start dates are described in Appendix A1.

Adverse event started more than 28 days after the last dose of IP will not be considered as a treatment-emergent AE.

4.2.8.2. Treatment-emergent Adverse Event Leading to Drug Withdrawal, Drug Interruption, or Death, and Drug-related Treatment-emergent Adverse Event

A TEAE leading to drug withdrawal is a TEAE for which the investigator indicates that the action taken with respect to IP is withdrawn permanently. A TEAE leading to drug interruption is a TEAE for which the investigator indicates that the action taken with respect to IP is interrupted. A TEAE leading to death is a TEAE for which the outcome is fatal. Relationship to IP is based on the investigator's causality judgment; that is, a drug-related AE is an AE indicated by the investigator to have a suspected relationship to IP.

4.2.8.3. Vital Signs and Weight

Vital signs and weight endpoints include:

- Observed value and change from baseline over time in vital signs (temperature, pulse, and blood pressure)
- Observed value, change and percent change from baseline over time in weight
- Shifts from baseline to post-baseline timepoints and to the worst post-baseline value in terms of normal/abnormal in pulse and blood pressure (normal ranges are defined as: 60-100 beats/minute for pulse, 90-140 mmHg for systolic blood pressure, and 60-90 mmHg for diastolic blood pressure)

4.2.8.4. Clinical Laboratory Evaluations

Laboratory evaluations include:

- Observed value and change from baseline over time in hematology and serum chemistry parameters
- Laboratory marked abnormalities (see Appendix A2)
- Shifts from baseline to post-baseline time points and to the worst post-baseline value in terms of normal/abnormal (low or high) in hematology and serum chemistry parameters

4.2.9 Derivations of Pharmacokinetic Endpoints

Not applicable.

4.2.10 Derivations of Pharmacodynamic Endpoints

Blood samples will be collected at Visit 2 (Baseline) and Week 16. Plasma proteins will be evaluated, such as but not limited to: IL-17A, IL-17F, and IL-22, as well as other markers for psoriasis and the mechanism of action for apremilast. The endpoints include observed values, changes and percent changes from baseline in biomarkers.

Derivations of rest of the pharmacodynamic endpoints including peripheral blood RNA gene expression, pharmacogenetic assessment and microbiome skin swab data will be specified in a PD analysis plan separately.

4.3. Randomization, Stratification, and Blinding

Approximately 574 subjects will be enrolled and randomized 1:1 to receive either apremilast 30 mg BID or placebo for the first 16 weeks. Subjects will be randomized based on a permuted block randomization using a centralized Interactive Response Technology (IRT). Randomization to apremilast arm or placebo arm will be stratified by baseline sPGA score (mild [2] or moderate [3]). Approximately 30% of subjects will be with sPGA score of mild (2) and approximately 70% of subjects will be with sPGA score of moderate (3). The IRT system will monitor the total enrollment of each stratum and screening will close once the approximate percentages are reached.

After all subjects have completed the Week 16 Visit (or discontinued from the study), a Week 16 database restriction will be performed; the primary data analysis will be conducted and a Week 16 CSR will be generated. However, unblinded data will only be made available to select CRO team members involved with analysis of the data and preparation of the Week 16 CSR. All other Sponsor, site, and CRO personnel directly involved with the conduct of the study will remain blinded to treatment assignments until the final database lock at the conclusion of the study.

4.4. Sample Size Determination

The sample size estimation is based on the results of the Phase 3 and 4 studies with apremilast. With a total of approximately 574 subjects and a randomization ratio of 1:1, the study will randomize approximately 287 subjects to apremilast 30 mg BID and 287 subjects to placebo. This sample size will provide more than 90% power to detect a 15% difference between the two treatment groups for the primary endpoint at a two-sided significance level of 0.05. The calculation is based on a chi-square test assuming 15% response rate for placebo and adjusting for a 20% dropout rate.

5. ANALYSIS PHASES OR PERIODS, DEFINITION OF ANALYSIS POPULATIONS, BASELINE AND TIME POINTS

5.1. Analysis Phases or Periods

For efficacy analysis, different phases will be used. For safety analysis, Placebo-controlled Phase and Apremilast-exposure Period will be used.

5.1.1. Analysis Phases

Per protocol specification, data summary and analysis will be provided for the following phases.

• Placebo-controlled Phase – Weeks 0 to 16

This phase starts on the day of randomization (Week 0/Visit 2), and stops on either: (1) the day the first IP for the next phase is dispensed at Week 16/Visit 7; or (2) the day of the discontinuation visit if the subject discontinued prior to or at Week 16/Visit 7; or (3) the last known study day if the subject is lost to follow-up prior to Week 16/Visit 7 during the phase.

For safety analysis in subjects who continued treatment in Apremilast Extension Phase (Weeks 16 to 32), the phase stopped one day prior to the first dose date in Apremilast Extension Phase.

For the analysis of measured (ie, visit-based) safety data (ie, labs, vital signs, and ECG), this period is exclusive of the date of the first dose of IP and inclusive of the date of the first Week 16 dose of Apremilast.

At the time of the Week 16 analysis, if the date of the first Week 16 dose of Apremilast (derived from the Study Drug Exposure eCRF which may not be entered by sites until the next visit after Week 16) is not yet available for subjects with Apremilast dispensed at Week 16 and on or before the (possibly derived) date of the last dose of IP as of the time of analysis (ie, no evidence that the subject has discontinued without receiving at least one dose of Apremilast after Week 16), the date of Apremilast dispensing at Week 16 will replace the date of the first Week 16 dose of Apremilast in the above definition for these subjects.

• Apremilast Extension Phase – Weeks 16 to 32

This phase starts on the day after the first IP is dispensed for the phase at Week 16/Visit 7, and stops on either: (1) the day of Week 32/Visit 10; or (2) the day of the discontinuation visit if the subject discontinued prior to or at Week 32/Visit 10; or (3) the last known study day if the subject is lost to follow-up prior to Week 32/Visit 10 during the phase.

For safety analysis, the phase started at the first dose date in the phase and ended at the last dose date + 1.

• Observational Follow-up Phase – 4 weeks

Subjects who complete the study or discontinue the study early, will be followed up for 28 days after the last dose of IP.

5.1.2. Apremilast-exposure Period for Safety Analysis

Apremilast-exposure Period will be used for safety analyses.

• Apremilast-exposure Period:

This period starts on the date of either: (1) the first dose of IP following randomization (Week 0/Visit 2) for subjects who are treated with apremilast from Week 0; or (2) the first dose of IP from the IP dispensed at Week16/Visit 7 for subjects who were originally treated with placebo and are treated with apremilast at Week 16.

This period stops on either: (1) data cut-off date; or (2) the end of the study.

5.1.3. Treatment Arms in Analysis Phases

In general, the treatment arms used in the analyses and summaries in each phase are described below in this section unless otherwise specified.

- Placebo-controlled Phase (Weeks 0 to 16)
 - Placebo
 - Apremilast 30 mg BID
 - Total (optional, not for the efficacy analysis)
- Apremilast Extension Phase (Weeks 16 to 32)

Subjects who entered the extension phase will be included in analysis, i.e, subjects who were initially randomized to apremilast and continued at Week 16 or who were initially randomized to placebo and switched to apremilast at Week 16.

- Placebo/30 mg BID
- 30 mg BID/30 mg BID
- Total
- Apremilast-exposure Period

Subjects who are treated with at least one dose of apremilast will be included here, which includes all subjects who are randomized to (at Week 0/Visit 2) or switched to (at Week 16/Visit 7) apremilast, and receive at least one dose of apremilast after randomization or Week 16.

- Placebo/30 mg BID
- 30 mg BID as Initiated
- 30 mg BID as Treated
- Observational Follow-up Phase (4 weeks)
 For subjects who entered Follow-up Phase from Placebo-controlled Phase, summaries will be provided by their initial treatment arm:

- Placebo
- 30 mg BID

For subjects who entered Follow-up Phase from Apremilast Extension Phase, summaries will be provided by their treatment sequence:

- Placebo/30 mg BID
- 30 mg BID/30 mg BID

5.2. Definition of analysis populations

5.2.1. Intent-to-treat Population

The intent-to-treat (ITT) population will consist of all subjects who are randomized regardless of whether or not the subject received IP. Subjects will be included in the treatment group to which they are randomized.

5.2.2. Per-protocol Population

The per protocol (PP) population will consist of all subjects included in the ITT population who receive at least one dose of IP, have both baseline and at least one post-treatment sPGA assessment, and have no important protocol deviations which may affect efficacy assessments in the Placebo-controlled Phase.

